3. an increased dose of corticosteroid before study week 8 and did not return to $<25\%$ above the baseline dose by week 12.

Endpoints:

1. **Primary Endpoint:**
 - a. Response rate at 40 weeks defined as percentage of patients meeting definition of improvement (DOI) in IIM patients treated with belimumab and standard therapy compared to the percentage of patients meeting DOI treated with placebo and standard therapy.
2. **Secondary Endpoints:**
 - a) Incidence of flares: flare rates during 40 weeks randomization period in patients with IIM treated with belimumab and patients treated with placebo and at week 64 in each group.
 - b) Time to achieve initial improvement defined as the time to reaching DOI.
 - c) Duration of improvement; quantified as the time from achieving improvement to the time of worsening or a disease flare. (Time from 1st DOI to 1st DOW or disease flare event). This will be based on the subset of subjects who achieve improvement.
 - d) Percent change in muscle enzyme levels (CPK and myoglobin) from baseline to week 40 and 64 in each respective group
 1. $<20\%$ reduction: no response
 2. 20-70% reduction: partial response
 3. $>70\%$ reduction: complete response
 - e) Percent change in manual muscle assessment (MMT-8) from baseline to week 40 and week 64 in each respective group.

- 1. <20% reduction: no response
- 2. 20-70% reduction: partial response
- 3. >70% reduction: complete response
- f) Percent change in prednisone dose from baseline to week 40 and week 64 in each respective group
- g) Proportion of subjects, among those on steroids at baseline, able to reduce the prednisone dose to ≤ 5 mg daily at week 40 and week 64 in each respective group.
- h) Flare rate in placebo group during the 40 week randomized treatment phase as compared to that group in the 20 week open label phase.
- i) Serious adverse event and adverse event rates
- j) Changes in B cell populations from baseline to week 40 and week 64
- k) Changes in autoantibody titers from baseline to week 40 and week 64
- l) Changes in immunoglobulin concentrations from baseline to week 40 and week 64

Inclusion Criteria:

Subjects enrolled in the study must meet the following inclusion criteria:

- 1) Adults ≥ 18 years of age
- 2) Have a diagnosis of:
 - a. definite or probable dermatomyositis (DM) by modified Bohan & Peter criteria or

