
1. For specific aim 1, the two treatment arms [B vs. P] will be compared with respect to the proportion of subjects who respond to treatment at 40 weeks (improvement according to definition), using either a chi-square test or Fisher’s exact test, as appropriate.
2. For specific aim 2, either a chi-square test or Fisher’s exact test, as appropriate, will be conducted to compare the proportion of subjects who had any flares during the 40-week randomized phase. For this analysis, each subject will be categorized at the end of 40 weeks as having had one or more flares or not having had any flares. In addition, we can also examine the total number of days that a subject had a specific flare during the course of the 40-week treatment, and compare the two treatment arms using the ‘Incidence density ratio’ method.
3. For specific aim 3, standard methods for survival analysis will be carried out. The Kaplan-Meier (KM) product limit method will be used to estimate overall “time-to-achieve (initial) response/improvement”. Ninety-five percent confidence intervals will be calculated using Greenwood’s formula for computing the standard error. Subjects who have not achieved improvement as of week 40 will be considered ‘censored’ for the event (event=improvement/response).
4. For specific aim 4, similar methods as indicated for specific aim 3 will be conducted. The analysis for this aim will be limited to the subset of subjects in each treatment arm who show improvement at anytime during the randomized phase of the trial. A subject who has not flared/worsened/relapsed as of week 40 will be considered ‘censored’ for the event (event=flare/relapse).
5. For specific aims 5, 6, 7, 9 and 10, each of the outcome variables of interest (uncensored continuous or categorical) will be analyzed separately, using a mixed model approach to repeated measures analysis of variance (MMRMANOVA) with the main effects of treatment arm (B vs. P), Disease type (PM vs DM), Disease Severity (Severe vs. Less Severe) and time (baseline vs. 40 weeks). If feasible, statistical interactions between

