treatment and time (baseline vs. week 40; or all available data at each study visit) or other factors of interest will be examined (e.g. Treatment X Disease Type; Treatment X Disease Severity). The treatment-by-time interaction term, will demonstrate whether the trajectories (or patterns of change) in the outcomes of interest are different between treatment groups. Data transformations may be used, in order to meet the necessary assumptions for the mixed models analyses. If transformations do not achieve the assumptions needed, a rank transformation or an appropriate non-parametric method will be considered.

If the analysis using a mixed model approach is not feasible due to the pattern of the data, then, a simplified analysis comparing the two treatment arms with respect to percent change (reductions) in muscle enzymes, MMT-8 and prednisone dose will be carried out using either a t-test or the Mann-Whitney test, as appropriate. A chi-square test or Fisher's exact test, as appropriate, may also be used if the continuous measures are grouped according to pre-specified categories (e.g. reduction in CPK will be categorized as No Response, Partial Response or Complete Response according to whether the percent reduction was <20% vs. 20%-70% vs. >70%, respectively).

6. For specific aim 8, the proportion of subjects who were able to reduce their daily prednisone dose to ≤ 5 mg at week 40, will be compared using either a chi-square test or Fisher's exact test, as appropriate.
7. For specific aim 11, either a chi-square test or Fisher's exact test, as appropriate, will be conducted to compare the proportion of subjects who experienced any SAEs or AEs during the randomized phase of the study. For this analysis, each subject will be categorized at the end of 40 weeks as having had any SAEs/AEs or not having any SAEs/AEs.

Multivariable analyses (logistic, cox) will be conducted for the above outcomes, if feasible. However, this may be limited by the sample size.

SAFETY DATA

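### For the secondary change outcomes, the term that tests a difference in change is optional and no test adjusts for baseline

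*Combined protocol and SAP*

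**What the plan says.** Specific aims 5, 6, 7, 9 and 10 each compare the arms on change from baseline to week 40. Statistical Methods, item 5, analyses all of them by a mixed model for repeated measures "with the main effects of treatment arm (B vs. P), Disease type (PM vs DM), Disease Severity (Severe vs. Less Severe) and time", time having the two levels baseline and week 40. Interactions come next, under a condition: "If feasible, statistical interactions between" "treatment and time (baseline vs. week 40; or all available data at each study visit"). Treatment by disease type and treatment by disease severity share that sentence and that condition. The item then says of the first of these: "The treatment-by-time interaction term, will demonstrate whether the trajectories (or patterns of change) in the outcomes of interest are different between treatment groups".

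If the mixed model proves unworkable, the plan substitutes "a simplified analysis comparing the two treatment arms with respect to percent change (reductions) in muscle enzymes, MMT-8 and prednisone dose", by t-test or Mann-Whitney test, or optionally by a chi-square or Fisher test on percent-change categories. This fallback covers aims 5 to 7 only. The closing line on multivariable analyses names logistic and Cox models, again conditionally, and does not mention baseline values.

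The matching secondary endpoints are defined on the percent scale: d) "Percent change in muscle enzyme levels (CPK and myoglobin) from baseline to week 40 and 64 in each respective group"; e) "Percent change in manual muscle assessment (MMT-8) from baseline to week 40 and week 64 in each respective group"; f) "Percent change in prednisone dose from baseline to week 40 and week 64 in each respective group".

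**The concern.** There are three linked problems.

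- **The deciding term is optional.** The only unconditional terms are main effects. With baseline in the response, a main effect of arm does not measure a difference in change. The term that does is grouped with exploratory subgroup interactions, although with two time points it costs one degree of freedom.
- **Baseline is never a covariate.** Even when the interaction is fitted, the two-time test reduces to comparing change scores. At low to moderate correlation this wastes information that the trial already collects, and there are only 15 patients per arm.
- **The fallback is unadjusted and on a fragile scale.** Percent change in prednisone is undefined for a patient with a zero baseline dose. Concurrent Medications and secondary endpoint g imply that such patients can enter. Inclusion criterion 8 can be read as requiring steroids. These places must be reconciled.

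At stake are the clarity and precision of the secondary results, not the false-positive rate.

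**Working it through.** **The plan's own figure.** The documents give no power or sample size for these outcomes. Their only such calculation is for the primary endpoint (5% vs 50%, two-sided alpha 0.05, 80% power). It reproduces: n = [1.96·√(2·0.275·0.725) + 0.8416·√(0.05·0.95 + 0.50·0.50)]² / 0.45² = 14.2, rounded up to 15 per group. It is not in dispute.

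**Inputs.** From Sample Size Considerations: 15 per arm. Assumed, because the documents give no values: equal SDs of 1 at baseline and week 40, correlation r between them, no true baseline difference, and a true week 40 difference d in SD units.

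**What each analysis estimates** (V is the per-patient variance; the standard error is √(2V/15)):

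- Main effects only: the arm term averages the two times, so it estimates (0 + d)/2 = d/2, with V = (1 + r)/2.
- Treatment-by-time, two times: it estimates d, with V = 2(1 − r). Disease type and severity are constant within a patient and cancel from the change, so this is the two-sample t-test on change.
- Baseline as covariate: it estimates d, with V = 1 − r².

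Worked case, d = 1 and r = 0.5, normal approximation:

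- Main effects: 0.5/√(2·0.75/15) = 1.58, power 35%.
- Change score: 1/√(2·1/15) = 2.74, power 78%.
- Baseline-adjusted: 1/√(2·0.75/15) = 3.16, power 89%.

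A simulation of 5,000 trials per scenario confirms the first point. The main-effects arm term averaged −0.50 for a true −1.00, with power 37 / 33 / 31% at r = 0.3 / 0.5 / 0.7.

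**Precision once the interaction is fitted.** The variance ratio, adjusted to change score, is (1 − r²)/(2(1 − r)) = (1 + r)/2 before the cost of estimating the slope. A simulation of 40,000 trials per cell included that cost. It compared a t-test on change (28 df) with week 40 regressed on treatment, baseline, disease type and severity (30 − 5 = 25 df). Balanced strata means identical stratum counts in both arms. Unbalanced means each factor drawn at random and unrelated to outcome; it is included because permuted blocks per site within four strata do not guarantee balance over 30 patients.

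| r | 0.3 | 0.5 | 0.7 | 0.8 | 0.9 |
|---|---|---|---|---|---|
| (1 + r)/2 | 0.65 | 0.75 | 0.85 | 0.90 | 0.95 |
| Simulated ratio, balanced | 0.68 | 0.78 | 0.88 | 0.94 | 0.99 |
| Simulated ratio, unbalanced | 0.73 | 0.84 | 0.96 | 1.01 | 1.07 |
| Power %, d = 1: change score | 61.1 | 75.2 | 92.7 | 98.7 | 100.0 |
| adjusted, balanced | 77.2 | 84.5 | 94.9 | 99.0 | 100.0 |
| adjusted, unbalanced | 74.2 | 82.0 | 93.3 | 98.3 | 100.0 |
| Power %, d = 0.8: change score | 43 | 56 | 78 | 91 | >99 |
| adjusted, balanced | 58 | 67 | 82 | 93 | >99 |
| adjusted, unbalanced | 55 | 63 | 79 | 91 | >99 |

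With d = 0, rejection was 4.7–5.3% for every test in the table. With baseline as the only covariate the ratio stays at the balanced values under either scheme, so ratios above 1 come from the added stratum terms.

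**Fallback, as illustration only.** For a lognormal outcome (assumed log SD 1) with d = 1 on the log scale, power at r = 0.3 / 0.5 / 0.7 was 38 / 56 / 84% for the t-test on percent change and 58 / 72 / 90% for Mann-Whitney. A baseline-adjusted test on the log scale gave 79 / 85 / 95%. How often the fallback would be used cannot be said, because its trigger is not specified.

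**Are the data there?** Study Procedures & Assessments and Appendix A schedule baseline and week 40 values for CPK, myoglobin, MMT-8, immunoglobulins (baseline at screening) and flow cytometry, taken here as the source of B cell counts. The plan already uses a baseline prednisone dose. Autoantibody titers have no scheduled collection, and BLyS is not named there.

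**The case against.** The strongest reply is that the intent is evident. The aims are about change, the plan itself says what the interaction is for, and nothing says a main-effects model would answer an aim. On that reading the condition is caution over a list that includes subgroup interactions. This makes a main-effects-only analysis less likely, but the text does not exclude it.

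Second, if every visit is used, MMT-8 has six times (Day 0 and weeks 8, 16, 24, 32 and 40), so the full interaction takes five degrees of freedom and some caution is reasonable. That is fair for the omnibus term, but the week 40 contrast is still one degree of freedom and can be named.

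Third, choosing baseline adjustment over change scores is an efficiency choice between valid tests, and its gain depends on a correlation nobody has stated. This stands, and it limits the point to secondary outcomes and to a recommendation.

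Fourth, for positive outcomes the ranks of percent change equal the ranks of log change, so the Mann-Whitney branch does not depend on the percent scale, and the fallback matches the percent-change endpoints. Both are true; what remains is the missing baseline adjustment and the zero-dose problem.

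Fifth, modelling week 40 prednisone dose in everyone brings in patients with no dose to reduce, which is not quite what endpoint f describes. This stands, so the analysis population for that endpoint must be stated.

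**Conclusion.** The concern holds. As written, the unconditional model does not test the change aims, the term that does is optional, and neither the mixed model nor its fallback adjusts for baseline. If the interaction were dropped, the arm term would target half the week 40 difference, with power of about 31–37% at 1 SD and correlations of 0.3–0.7. If it is fitted, the remaining loss against baseline adjustment at 1 SD is about 13–16 points of power at correlation 0.3, 7–9 at 0.5 and 1–2 at 0.7. At 0.8–0.9 it is absent or slightly reversed. These sizes rest on assumed effects, correlations, normality and equal SDs; the half-effect result and the direction at low to moderate correlation are the firm parts. Type I error, the primary test and the sample size are not affected. It is worth correcting before analysis but is not critical to the trial.

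**What to change.** In Statistical Methods, item 5:

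1. Name the week 40 treatment contrast as the test for each outcome, without a feasibility condition. Take it from a model of the week 40 value, or of the post-baseline visits with treatment-by-visit, adjusted for baseline value, disease type and severity, on a log or rank scale where needed.
2. Keep the feasibility condition only for the treatment by disease type and treatment by severity interactions.
3. In the fallback for aims 5 to 7, use ANCOVA or rank ANCOVA for the between-arm test.
4. Still report percent change and its categories for endpoints d to f. Where all values are positive, back-transform log-scale results to a percent difference.
5. Analyse prednisone as dose adjusted for baseline dose, state which patients are included, and reconcile the passages on steroid use at entry.

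The cost is SAP wording, one degree of freedom for the baseline covariate, and a sentence separating what is reported (percent change) from what is tested (the baseline-adjusted contrast). No new data are needed for CPK, myoglobin, MMT-8, prednisone dose, immunoglobulins or B cells. Autoantibody titers would first need a scheduled collection.

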There will be no formal interim analyses or formal statistical stopping rules. However, statistical summaries of adverse event rates using 95% exact confidence intervals will be provided to the data safety monitoring board as need. During regular bi-annual meetings the data safety monitoring board will evaluate the overall rate of adverse events and unanticipated problems. Upon review the group will determine whether there are any changes needed to the anticipated benefit-to-risk assessment and if the study should continue. The results of these regular meetings will be recorded and disseminated to the other participating clinical sites. Safety data will be collected in the form of adverse events (AEs), serious AEs (SAEs) and laboratory parameters (e.g., hematology, chemistry, etc.). AEs will be recorded with the date of onset, severity, relationship to study drug, and disposition. AEs will be translated into a standard classification system such as COSTART or MedDRA. AE data will be summarized according to incidence rates, by treatment arm and by whether or not the AE was treatment related. AEs will be summarized using descriptive statistics and tabulated according to treatment group for each strata. The AE report will be descriptive, rather than inferential.

SAMPLE SIZE CONSIDERATIONS

We plan to enroll 30 evaluable patients with 15 in each of two treatment arms [B vs. P].

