From available trials in IIM, there is an observed placebo effect of 0%-40% at 12 weeks^{9,10} and 0% at 52 weeks⁹. These results demonstrate that the placebo response rate at 40 weeks can be very variable. One clinical study looking at rituximab in myositis was the first prospective, double-blind, randomized trial in myositis and the largest clinical trial ever performed in the inflammatory myopathies¹⁶. This trial employed a unique design; subjects were divided into two groups: early-start and delayed-start of rituximab. Overall, 83% of enrolled subjects (with severe refractory disease) met the DOI by the end of the trial, despite lack of statistical significance between groups. An alternate double-blind, placebo-controlled trial of etanercept (50 mg subcutaneously weekly for 52 weeks) where 16 subjects were randomized showed that: all 5 subjects receiving placebo were treatment failures (median time to treatment failure: 148 days)¹⁷. In contrast, 5 of 11 subjects in the etanercept arm were successfully weaned off prednisone; the median time to treatment failure in this group was 358 days ($p = 0.0002$). This data shows that for myositis trials, placebo response is often close to 0%. In order to achieve a clinically meaningful difference between study treatment arms, the response rate of the treatment group would need to be at least 50%.

We hypothesize (optimistically) the response rate at 40 weeks in the placebo arm to be 5%. We further assume that a magnitude of difference of 45% would be clinically meaningful (this corresponds to a 50% response rate in the Belimumab arm).

Based on the assumption that a difference of 45% in response rates at 40 weeks between Placebo and the investigational agent, Belimumab, would be clinically meaningful, then, a two group chi-square test ($\alpha=0.05$, two sided test) will yield 80% power to detect a difference between the Placebo arm week 40 response rate of 5% and a Belimumab-treated arm week 40 response rate of 50% (Odds ratio=19) when the sample size in each group is 15, assuming the dropout rate is 0%.

Table 1 below shows the sample size requirements for various pairs of (hypothesized) 40-week response rates and assumptions on what would be a clinically meaningful difference between treatment arms. Corresponding sample sizes are provided for the specified range of parameters. Calculations were based on a two-sided chi-square test to achieve 80% power ($\alpha=0.05$).

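### If the no/partial/complete enzyme grades are tested between arms, the only tests named for them ignore the ordering; naming an ordered test is a cheap improvement

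*Combined protocol and SAP*

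**What the plan says.** In the Endpoints section, secondary endpoint d is "Percent change in muscle enzyme levels (CPK and myoglobin) from baseline to week 40 and 64 in each respective group". It is followed by three grades: below 20% reduction is no response, 20 to 70% is partial, and above 70% is complete. Endpoint e attaches the same three grades to MMT-8.

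Statistical Methods, item 5, sets out the analysis of these change outcomes in layers:

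- First, a repeated-measures mixed model, in which "each of the outcome variables of interest (uncensored continuous or categorical) will be analyzed separately". If its assumptions fail, the plan allows transformation, rank transformation or a non-parametric method.
- Second, if the mixed model is not feasible, a comparison of percent change that "will be carried out using either a t-test or the Mann-Whitney test, as appropriate".
- Third, in the same fallback paragraph, a chi-square or Fisher's exact test "may also be used if the continuous measures are grouped according to pre-specified categories". The example given is CPK graded "according to whether the percent reduction was <20% vs. 20%-70% vs. >70%, respectively".

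No trend test, ordinal rank test or proportional-odds model is named for the graded form. On size, Sample Size Considerations says "We plan to enroll 30 evaluable patients with 15 in each of two treatment arms".

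**The concern.** The grades run from worse to better. A chi-square or Fisher test on the resulting 2 x 3 table gives the same p-value however the three columns are relabelled. It therefore cannot tell a consistent move up the scale from a reshuffle with no direction. That is a property of the tests and needs no assumption about the data.

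At stake is some power in a small secondary comparison, and a clear reading of any graded result that is reported. With 30 patients, a general test that spends its sensitivity on patterns of little interest is less suited to the question the grades pose, which is whether patients move up. The plan also leaves open whether the grades will be tested at all.

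**Working it through.** **The plan's own figure.** The only power statement is for the binary primary endpoint: 5% against 50%, 15 per arm, two-sided alpha 0.05. The section states that "Calculations were based on a two-sided chi-square test to achieve 80% power". Using the normal formula without continuity correction, with mean proportion (0.05 + 0.50)/2 = 0.275:

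n = [1.960·√(2 × 0.275 × 0.725) + 0.842·√(0.05 × 0.95 + 0.50 × 0.50)]² / 0.45² = 14.2, so 15 per arm. Power at 15 per arm is 82.3%. The figure reproduces. No power and no expected proportions are given for the three grades.

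**Inputs for the graded comparison.** From the documents: 15 per arm and three ordered grades. Assumed: two-sided alpha 0.05 (stated only for the primary endpoint), and every grade distribution below.

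**Method.** Each arm has 136 possible three-grade outcomes, so all 136 × 136 pairs were enumerated and weighted by their multinomial probabilities. Given the column totals m₁, m₂, m₃, a table with arm counts x₁, x₂, x₃ has probability ∏C(m_k, x_k)/C(30, 15).

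- Fisher (Freeman-Halton form) sums this over tables no more probable than the one observed.
- The exact Mann-Whitney test sums it over tables whose mid-rank sum lies at least as far from its null mean.
- Pearson chi-square uses 2 degrees of freedom when all three grades occur.

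**Main example (assumed).** Placebo 60/30/10%, belimumab 20/40/40%. The odds of at least partial response are 0.4/0.6 against 0.8/0.2, a ratio of 6. The odds of complete response are 0.1/0.9 against 0.4/0.6, again 6. So this is a proportional-odds shift. Power:

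- Fisher 57.5%, chi-square 61.1%
- exact Mann-Whitney 67.5%, asymptotic Mann-Whitney 71.6%

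Exact against exact, the gain is 67.5 − 57.5 = 10.0 points. Asymptotic against asymptotic, it is 71.6 − 61.1 = 10.5. Exact Mann-Whitney against asymptotic chi-square gains less: 67.5 − 61.1 = 6.4.

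**Range.** Seven placebo distributions were used (60/30/10, 70/20/10, 50/35/15, 80/15/5, 40/40/20, equal thirds, 60/20/20), each with a proportional-odds shift. Gains in points:

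| Odds ratio | Mann-Whitney − chi-square (both asymptotic) | Mann-Whitney − Fisher (both exact) |
|---|---|---|
| 3 | 7.0–7.8 | 3.6–6.8 |
| 4 | 9.1–10.6 | 6.6–9.2 |
| 6 | 9.6–11.7 | 8.0–10.0 |
| 8 | 8.1–10.1 | 7.0–9.2 |
| 10 | 6.5–8.6 | 5.8–8.0 |
| 19 | 2.2–4.9 | 2.2–4.6 |

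Hence about 2 to 12 points, like for like.

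**Size.** Under two null cases (50/30/20 and 80/15/5) the exact Mann-Whitney test rejects 3.8% and 2.0% of the time, against 5.3% and 3.5% for chi-square. The gain of the exact test is not bought with type I error.

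**Where the gain shrinks or reverses** (Fisher / chi-square / exact Mann-Whitney, %):

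- Very sparse placebo grades, 95/4/1 with odds ratio 8: 27.4 / 32.0 / 27.8. The gain over Fisher is 0.4, and chi-square is ahead.
- Nobody in the top grade, 95/5/0 v 50/50/0: 73.6 / 87.0 / 73.6. There is no gain over Fisher.
- Benefit almost wholly from none to partial: 60/30/10 v 25/65/10 gives 43 / 44 / 35; 80/15/5 v 40/55/5 gives 55 / 59 / 48; 90/5/5 v 50/40/10 gives 64 / 67 / 57. The loss runs from 55 − 48 = 7 to 59 − 48 = 11 points.
- A pattern with no single direction, 50/20/30 v 20/60/20: 51.8 / 54.5 / 14.2.

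**The case against.** The strongest objection is that the plan does not rest on the graded table. The chi-square or Fisher test is permitted, not required. It comes behind a mixed model and a t-test or Mann-Whitney test on the ungrouped change. A simulated Mann-Whitney test on ungrouped values has about 76% power at odds ratio 6 (latent logistic shift, 20,000 runs), above every grouped test in the main example. This stands. A reader might infer that the plan's main enzyme comparison gives away power or discards direction; the documents do not support that.

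A reader might also infer that item 5 puts a percent-reduction grade, which has no baseline value, into a model with a baseline time point. The text does not say so. Its mention of categorical outcomes covers aims 5, 6, 7, 9 and 10 together, and the grades are linked only to chi-square or Fisher. A categorical outcome such as an autoantibody titre can have a baseline value. There is no ground here for restricting the mixed model to continuous outcomes.

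It is also fair to say that an ordered test is not uniformly better, as the last set of cases shows. That stands as a real cost. What survives is narrower: the grades are part of the endpoint definition, they ask whether patients move up, and the plan names no test for them that uses that order.

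**Conclusion.** The point holds as a cheap improvement to an optional secondary analysis. If the CPK or myoglobin grades are compared between arms, the named tests ignore their order. Under a shift that moves both cut-points, an ordered test gains about 2 to 12 points like for like at 15 per arm. The exact Mann-Whitney margin over asymptotic chi-square is smaller, 6.4 points in the main example.

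The size rests on assumed grade distributions and an assumed alpha of 0.05 for a secondary outcome. It would be wrong to quote any single figure as the power this trial loses, because the documents give no proportions from which to derive one. The gain can vanish with sparse upper grades, and it reverses if benefit stops at partial response or runs in no single direction. The binary primary endpoint and the analyses of continuous change are untouched.

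**What to change.** In Statistical Methods, item 5, replace the chi-square or Fisher option for the graded enzyme outcomes with wording such as: *If the CPK or myoglobin response grades are compared between arms, an exact two-sided Mann-Whitney (linear-by-linear) test on the ordered grades will be used. Otherwise the grades will be reported descriptively, and inference will rest on the continuous percent change.*

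This costs one sentence and no new data, and should be settled before unblinding. The price is the lower power, shown above, for effects confined to the partial grade or without a consistent direction. Stratifying this test by disease type and severity is not part of the proposal: it would split 30 patients over four strata, and none of the powers above were computed that way.

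Before the same test is applied to MMT-8, endpoint e must be reconciled with the Core Set Measures definition. Endpoint e counts a large reduction in the score as complete response, while the Core Set Measures treat a low score (125 or below out of 150) as active disease. An ordered test would inherit whichever direction the grades are given.
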